### 13.3. Study design, primary endpoint analysis plans and power:

To test these hypotheses, we propose a single arm, two-stage phase II trial of single agent trametinib in advanced TNBC patients, followed by trametinib in combination

with AKT inhibitor GSK2141795 at time of tumor progression (Figure 1, [Schema](#)). This design was chosen because trametinib monotherapy is more tolerable than trametinib in combination with GSK2141795, and therefore, it is vital to first assess if there is a subpopulation of TNBC patients (such as those that are PTEN wild type) that will derive benefit from anti-MEK therapy alone before exposing patients to dual MEK and AKT inhibition. GSK2141795 will be added at time of tumor progression to determine if the addition of AKT inhibition will overcome the primary proposed mechanism of resistance to trametinib through blockade of the PI3K/AKT pathway.

The goals of this study are to evaluate whether or not trametinib alone provides sufficient clinical response in this patient population (Part 1), and to evaluate if the combination of trametinib plus GSK2141795 in patients who progress will improve the objective response in this patient population (Part 2). To minimize the expected number of subjects treated if the trametinib monotherapy is not sufficiently active in this setting, a Simon two-stage Optimum Design will be used for Part 1 that allows for early termination of accrual if insufficient activity with monotherapy is observed. In addition, upon completion of Part 1 of this study we will further evaluate the combination of trametinib plus GSK2141795 in those patients in Part 1 who progress (Part 2). Similarly, to limit the number of patients accrued if this combination regimen proves to be insufficiently active, we will utilize a Fleming Two-Stage Design. As in any two-stage design, the 2nd stage will only commence and accrue additional patients if the specified decision criteria are met for the 1st stage. Even though Part 2 is directly linked to Part 1 (in the fact that those who progress on Part 1 are able to go on to Part 2) each part will have its own study design and decision criteria associated with them. The primary evaluation and goal of interest is Part 1, where the Part 2 evaluation is a secondary goal of this trial.

For Part 1: We hypothesize that the true ORR with monotherapy is at least 20% versus a null hypothesis that the ORR is at most 5%, reflecting that any treatment success (clinical response) is due to chance alone. Under this Simon Optimal two-stage design, we aim to test the null hypothesis  $H_0: \text{ORR} \leq 5\%$  vs.  $H_1: \text{ORR} \geq 20\%$  to evaluate the efficacy of trametinib monotherapy. With 90% power and a Type I error rate of 10%, the interim analysis for this design requires that at least one patient of the first 12 evaluable patients enrolled have observed objective response (CR+PR); otherwise, if no patients have an objective response to treatment, then we will consider this sufficient early evidence that this treatment regimen is not worth pursuing further as monotherapy. At this point, we will evaluate the combination regimen in Part 2 in any patients subsequently enrolled on the trial and not just those who fail monotherapy in Part 1. If at least 1 patient has clinical response out of the first 12 enrolled patients treated with combination therapy, we will continue accrual to the second stage and accrue an additional 25 patients for a total of 37 patients. In the final analysis, we would need to see at least 4 patients with clinical response as defined above out of the first 37 evaluable patients accrued to determine that this monotherapy has promising associated activity and thus is worth pursuing further. Otherwise, if 3 or fewer have clinical benefit, then we will consider this monotherapy to not be sufficiently active on its own.

For Part 2: In this part of the trial, we will focus on evaluating the ability to obtain clinical response in those patients in Part 1 who progress on monotherapy; we expect that about 80% of patients will progress and remain free of limiting toxicity to go on to Part 2. With our planned over-accrual and if all are evaluable, we will have 32 patients available for this portion of the trial. If we observe issues with patients going off study during Part 1, the study team will discuss with CTEP potential solutions and if patients who cannot tolerate the MEK inhibitor as single agent therapy will be replaced in the overall sample size to facilitate subsequent evaluation of the combination regimen in Part 2. However, in evaluation of the primary outcome of the MEK inhibitor as single agent therapy, any such patient who is unable to tolerate therapy and/or goes off study during Part 1 will still be included in the analyses and decision rule evaluations.

Since this is also a relapsed/refractory setting, our goals are the same as those in Part 1. Therefore, we hypothesize that the objective response rate of this combination therapy is at least 20% versus the null hypothesis that it is at most 5%. With 90% power and a Type I error rate of 10%, this Fleming two-stage design has an interim analysis after the first 16 evaluable patients are accrued. If no patients have documented objective response (CR+PR) out of the first 16 enrolled patients the trial cohort then we will consider this sufficient early evidence that this is not a promising regimen and accrual will be terminated. If at least 1 patient has clinical response out of the first 16 enrolled patients, then accrual will continue and an additional 16 patients will be accrued for a total 32 evaluable patients. In the final analysis, if at least 4 patients have clinical response as defined above, then we will consider this a promising regimen and worthy of further study.

Assuming that the number of responses is binomially distributed, we will estimate objective response rates independently for parts 1 and 2, and generate corresponding 95% binomial confidence intervals.

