### 1.2. Secondary Objectives

- To assess the anti-tumor activity associated with trametinib in combination with AKT inhibitor GSK2141795 after progression on trametinib in patients with metastatic TNBC.
- To determine the progression-free survival following the initiation of treatment with trametinib monotherapy in patients with metastatic TNBC.
- To determine the progression-free survival following the initiation of treatment with trametinib in combination with GSK2141795 in patients with metastatic TNBC.
- To determine the overall survival following the initiation of treatment with trametinib with GSK214179 in patients with metastatic TNBC.
- To determine the nature and degree of toxicities associated with trametinib monotherapy and trametinib in combination with GSK2141795 in patients with metastatic TNBC.
- To determine the biomarker potential of PTEN to predict response to single agent trametinib
- To determine molecular markers of sensitivity and resistance to trametinib monotherapy and trametinib in combination with GSK2141795 in patients with metastatic TNBC.

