## **13 STATISTICAL CONSIDERATIONS**

### **13.1 Study Overview**

This is an open label, two-stage phase II study designed to assess the proportion of patients who have a partial or complete response to treatment with trametinib in advanced TNBC patients, followed by trametinib in combination with AKT inhibitor GSK2141795 at time of tumor progression (Figure 1, [Schema](#)). Preclinical data from the Ohio State University and others suggest that a subset of triple negative breast cancer (TNBC) patients that are PTEN wild type may demonstrate sensitivity to single agent MEK inhibition (Unpublished [name], [name]), and dual targeting of the RAS/RAF/MEK/ERK pathway and PI3K/AKT pathways may result in durable response after progression on MEK inhibitor monotherapy. Therefore, we have two parts to this study, where the primary driving hypotheses are two-fold: (1) that the anti-tumor response to the single agent trametinib will depend on the PTEN status of the tumor, with wild type PTEN having a higher likelihood of response than PTEN

null tumors; and (2) that simultaneous inhibition of the RAS/RAF/MEK and PI3K/AKT pathway with trametinib and GSK2141795 will overcome both intrinsic and acquired resistance to trametinib monotherapy. In addition to evaluating clinical efficacy of this regimen, we will also assess correlative markers in relation to clinical outcomes of interest. Part 1 focuses on evaluation of efficacy after treatment with single agent trametinib, and Part 2 is focused on evaluating salvage efficacy of treatment with the combination of trametinib and GSK2141795 in patients who progress on trametinib alone.

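### The primary decision text names two evaluable totals (45 and 37) and the wrong treatment at the stage-two gate; if Part 1 stops at 0/12, Part 2 also lacks a response rate split by prior trametinib

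*Combined protocol and SAP*

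**What the plan says.** **Part 1, number of patients.** Section 13.2 requires between 12 and 37 evaluable patients. It then says that the decision analysis for this part uses the first 45 evaluable patients. Its closing paragraph reports that 50 patients were consented so that 37 evaluable patients could be enrolled. Section 13.3 takes the final decision on the first 37 evaluable patients.

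**Part 1, rule.** Section 13.3 sets a Simon optimal two-stage design. The null response rate is at most 5% and the alternative at least 20%, with type I error 10% and power 90%. The study stops if none of the first 12 evaluable patients responds. Otherwise 25 more are accrued, and at least 4 responders of 37 are needed. The sentence that opens the second stage counts responses among 12 patients on the combination. The sentences that follow it draw the conclusion about monotherapy.

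**If none of the 12 responds.** Section 13.3 says "we will evaluate the combination regimen in Part 2 in any patients subsequently enrolled on the trial and not just those who fail monotherapy".

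**Part 2.** Section 13.3 states that "each part will have its own study design and decision criteria associated with them". The Part 2 population is "those patients in Part 1 who progress on monotherapy". The objective in section 1.2 is activity of trametinib "in combination with AKT inhibitor GSK2141795 after progression on trametinib in patients with metastatic TNBC", and section 13.1 describes "evaluating salvage efficacy of treatment with the combination of trametinib and GSK2141795 in patients who progress on trametinib alone". The rule stops at 0/16; otherwise accrual goes on to 32, and with at least 4 responders "then we will consider this a promising regimen and worthy of further study". On estimation, "we will estimate objective response rates independently for parts 1 and 2". No response rate by prior trametinib is specified.

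**The concern.** The first matter concerns the primary endpoint. A decision rule needs one denominator and one treatment. Section 13.2 gives a denominator that conflicts with its own maximum and with section 13.3. The stage-two sentence names a treatment other than the one the rule tests. An analyst who followed section 13.2 with the cut-off in section 13.3 would apply a test that no longer holds its stated error rate.

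The second matter is conditional. After 0/12, patients who have never had trametinib enter Part 2, while every statement of Part 2's purpose concerns patients who progressed on it. The plan does not say which rule covers the new entrants. If they come under the single 16/32 rule and the single response rate, Part 2 could be positive, and be read as activity after progression, with no responder among the progressed patients.

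**Working it through.** **1. The plan's own Part 1 figures.** Inputs from section 13.3: null rate 0.05, alternative 0.20, stop at 0 of 12, success at 4 or more responders. With X binomial and n the final total:

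P(success) = P(Xₙ ≥ 4) − P(0 of 12) × P(Xₙ₋₁₂ ≥ 4)

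| Final total | True rate | Calculation | Result |
|---|---|---|---|
| 37 | 5% | 0.1119 − 0.5404 × 0.0341 | 0.0935 |
| 37 | 20% | 0.9550 − 0.0687 × 0.7660 | 0.9024 |
| 45 | 5% | 0.1866 − 0.5404 × 0.0808 | 0.1430 |
| 45 | 20% | 0.9871 − 0.0687 × 0.9192 | 0.9239 |

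The 37-patient rule reproduces the stated 10% and 90%. A search over two-stage designs meeting those limits returns the same design (0/12, then at least 4/37) as the one with the smallest expected sample size under the null, 23.5. The 45-patient total with the same cut-off exceeds 10%. Arithmetically 45 = 0.9 × 50, which may be its origin, but the documents do not say so.

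**2. Treatment named at the gate.** The gate's numbers (12, then 25 more, total 37) are those of the monotherapy design just reproduced. Part 2's numbers are 16, 16 and 32. The conclusion drawn from 37 patients is about monotherapy. The combination fits neither the numbers nor the conclusion.

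**3. The 0/12 branch.** P(0 of 12) = (1 − p)¹², which is 54%, 28% and 6.9% at monotherapy response rates of 5%, 10% and 20%.

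Part 2 as planned (0/16 stop, at least 4/32) gives type I error 7.1% and power 89.6% when all 32 patients share one rate.

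Assumptions for a mixed Part 2, none of them in the documents except the 80% expected to go on to Part 2:
- about 10 progressed patients (0.8 × 12 = 9.6), entering first, response rate 5%;
- 22 trametinib-naive patients, response rate q of 10% or 20%;
- accrual pauses at the Part 1 interim.

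The first 16 are then 10 progressed and 6 naive patients. With Y the number of naive responders:

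P(positive, no progressed responder) = 0.95¹⁰ × [P(Y₂₂ ≥ 4) − (1 − q)⁶ × P(Y₁₆ ≥ 4)]

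- q = 10%: 0.5987 × (0.1719 − 0.5314 × 0.0684) = 0.081
- q = 20%: 0.5987 × (0.6680 − 0.2621 × 0.4019) = 0.337

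Multiplied by P(0 of 12):

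| Monotherapy rate | q = 10% | q = 20% |
|---|---|---|
| 5% | 4.4% | 18% |
| 10% | 2.3% | 9.5% |
| 20% | 0.6% | 2.3% |

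If 16 or more progressed patients enter first, the first 16 are all progressed. No responder among them triggers the 0/16 stop, so the probability is zero. Patients started on monotherapy while the interim was pending would push the mix that way.

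**The case against.** **On 45.** The closing paragraph of section 13.2 already shows that 37 is meant. With 37 evaluable patients a decision on 45 cannot be taken. That stands. A reader might infer that the trial ran at 14.3% type I error; the documents do not support this. The figure shows only why 45 cannot be paired with the written cut-off, and no new cut-off for 45 is needed. The sentence is still a wrong instruction for the primary decision.

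**On pooling.** The plan never says in words that naive patients come under the 16/32 rule. Read literally, the stage-two sentence could be a separate 12/37 rule for the patients just admitted to the combination. This also stands as far as it goes: pooling is an inference from one rule and one estimate per part, and it depends on treating the combination wording as a slip. The match in numbers and the monotherapy conclusion make a slip the better reading, but the sponsor must confirm it.

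**On error rates.** Under the assumptions above, the overall chance of a positive Part 2 on the branch is 26% at a naive rate of 10% and 69% at 20%. A reader might take these for false-positive rates. They mostly are not: the hypothesis concerns the combination's response rate, and success means a promising regimen, which naive responders can fairly support.

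**On resistance.** A reader might equate response after progression with overcoming acquired resistance. Section 13.1 says the combination "will overcome both intrinsic and acquired resistance to trametinib monotherapy", naming both kinds. On this branch none of the 12 patients who decided the interim responded to trametinib, so their progression may be largely intrinsic resistance.

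**Conclusion.** The primary decision text is wrong as written in two places, whatever the course of the trial. The 45 in section 13.2 contradicts the maximum of 37, the reported 37 and the rule in section 13.3; only 37 gives the stated design (9.3% and 90.2%). The stage-two gate names a treatment that does not fit its own rule. Both are errors of wording in a decision rule, not evidence of a faulty design.

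The Part 2 point is secondary and holds only if Part 1 stops at 0/12; the documents do not say whether it did. On that branch the governing rule is unclear, and the after-progression objective has no estimate of its own. The specific harm, a positive result with no progressed responder, is about 8% or 34% given the branch, and about 4% or 18% jointly with 0/12 at a monotherapy rate of 5%. These sizes rest on the assumed 10/22 split, order of entry and response rates, and fall to zero when 16 or more progressed patients enter first. Part 2 is itself a secondary goal.

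**What to change.** 1. In section 13.2, replace 45 with 37.
2. In section 13.3, Part 1, reconcile the combination wording in the stage-two sentence with the monotherapy rule whose numbers it carries. State which rule covers patients started directly on the combination after 0/12.
3. In section 13.3 or 13.4, add that if Part 1 stops at 0/12, the Part 2 response rate with exact 95% confidence interval is reported separately for patients who progressed on trametinib and for those started directly on the combination. Statements on the after-progression objective rest on the progressed patients alone and are not described as showing acquired resistance. The pooled 16/32 rule may stay as support for a promising regimen.

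The cost is wording only, with no change to sample size or cut-offs. The progressed group would be descriptive: with 10 patients the exact 95% interval is 0 to 31% for no responders and 0.3 to 45% for one.

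### The sentence that opens stage 2 of the Part 1 monotherapy test counts responses on the combination, contradicting the interim rule stated just before it

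*Combined protocol and SAP*

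**What the plan says.** All of this is in Section 13.3. The general design text assigns the Simon optimal design to monotherapy in Part 1 and a Fleming design to the combination in Part 2. It says that "each part will have its own study design and decision criteria associated with them" and that "the 2nd stage will only commence and accrue additional patients if the specified decision criteria are met for the 1st stage".

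The Part 1 paragraph then runs in this order:

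1. The hypotheses concern the response rate on monotherapy: at most 5% against at least 20%, with type I error 10% and power 90%.
2. The interim analysis "requires that at least one patient of the first 12 evaluable patients enrolled have observed objective response (CR+PR"). With no responder, the regimen is judged not worth pursuing as monotherapy.
3. The failure branch continues: "At this point, we will evaluate the combination regimen in Part 2 in any patients subsequently enrolled on the trial".
4. The stage 2 sentence asks for at least one response "out of the first 12 enrolled patients treated with combination therapy, we will continue accrual to the second stage", adding 25 patients for a total of 37.
5. The final rule asks for at least 4 responders in 37 evaluable patients "to determine that this monotherapy has promising associated activity and thus is worth pursuing further".
6. The failing outcome reads: "Otherwise, if 3 or fewer have clinical benefit, then we will consider this monotherapy to not be sufficiently active on its own".

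For Part 2, "this Fleming two-stage design has an interim analysis after the first 16 evaluable patients are accrued". At least 1 response leads to 16 more patients, 32 in total, and at least 4 responses make the regimen promising.

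**The concern.** Item 4 is the only sentence that explicitly opens stage 2 with numbers attached, and it names a regimen that Part 1 does not test. It can be read in two ways.

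- **(a) As the Part 1 gate.** It then contradicts item 2, because it counts responses to the combination, and in enrolled rather than evaluable patients.
- **(b) As a rule for patients started on the combination after a failed monotherapy interim.** Item 3 comes directly before it and supports this reading. It then gives the combination a 12+25=37 plan while Part 2 gives it 16+16=32. The verdict that follows in the Part 1 paragraph is still on monotherapy, so that paragraph sets no final cut-off for these patients.

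The rule decides whether accrual continues and whether the primary objective is met. The stated error rates belong to a gate on monotherapy responses. Under (a) they would depend on how active a different regimen is. Under (b) two interim rules would govern the combination.

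A smaller point of terminology: the success branch counts clinical responses and the failure branch counts clinical benefit, which Section 13.4 defines as a rate that includes stable disease.

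**Working it through.** **Inputs from Section 13.3.** Null and alternative response rates 0.05 and 0.20. Part 1: n1 = 12, continue with at least 1 response, N = 37, success with at least 4. Part 2: n1 = 16, continue with at least 1, N = 32, success with at least 4.

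**Input not in the documents.** The combination response rate, pc, is taken as 5%, 10%, 20% and 30%. Responses to the two regimens are treated as independent.

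**1. The plan's own figure.** With X the number of responders and the gate on monotherapy:

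P(success) = P(X ≥ 4 of 37) − P(0 of 12) × P(X ≥ 4 of 25)

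- At 5%: 0.1119 − 0.5404 × 0.0341 = 0.0935.
- At 20%: 0.9550 − 0.0687 × 0.7660 = 0.902.

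Both meet the stated 10% and 90%. Expected sample size at 5% is 12 + (1 − 0.540) × 25 = 23.5. An exhaustive search over N from 10 to 50 for these error limits returns 0/12, 3/37 as the Simon optimal design. The numbers 12, 25 and 37 therefore belong to the monotherapy test.

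**2. The Part 2 rule for comparison.** 0/16 then 3/32 gives type I error 0.0707 and power 0.896. It is a separate design and does not contain 12 or 37.

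**3. Reading (a).** The combination gate is passed with probability G = 1 − (1 − pc)^12. If it replaces the monotherapy gate, Part 1 success has probability G × P(X ≥ 4 of 37). If both gates apply, it is G times the two-stage value from step 1.

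| pc | G | Type I error, replaced | Power, replaced | Type I error, both | Power, both |
|---|---|---|---|---|---|
| 5% | 0.4596 | 0.051 | 0.439 | 0.043 | 0.415 |
| 10% | 0.7176 | 0.080 | 0.685 | 0.067 | 0.648 |
| 20% | 0.9313 | 0.104 | 0.889 | 0.087 | 0.840 |
| 30% | 0.9862 | 0.110 | 0.942 | 0.092 | 0.890 |

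With replacement, type I error passes 10% when 0.1119 × G > 0.10, that is when pc exceeds about 17%.

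**4. Reading (b).** Probability of stopping at the combination interim:

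- 12 patients: 0.95^12 = 0.540 at 5%, and 0.80^12 = 0.069 at 20%.
- 16 patients: 0.95^16 = 0.440 at 5%, and 0.80^16 = 0.028 at 20%.

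The 12-patient rule stops where the 16-patient rule continues with probability (1 − p)^12 × [1 − (1 − p)^4], which is 0.100 at 5% and 0.041 at 20%. The totals also differ, 37 against 32.

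**The case against.** The strongest reply is that nobody would be misled about Part 1. The hypotheses, the interim rule and the final verdict all concern monotherapy, and the numbers reproduce the Simon optimal design exactly. This stands, and it is why the point is a wording correction.

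The reading (a) figures can also be called hypothetical. Part 2 expects about 80% of patients to go on to the combination, so 12 stage 1 patients would supply about 0.8 × 12 = 9.6. The chance that all 12 reach it is 0.8^12 = 0.07 if patients are independent, and filling the gate would take about 12/0.8 = 15 Part 1 patients. Independence is doubtful too, since Part 2 patients are largely the same people after progression. This also stands: the table shows what the literal wording would imply and does not forecast this trial's error rates.

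Three smaller points are fair. Part 2 mixes enrolled and evaluable in the same way, so that word alone proves little. The word otherwise marks the clinical benefit phrase as a probable slip. Part 2 does give a final cut-off, at least 4 of 32, so the gap under reading (b) is only within the Part 1 paragraph.

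Section 13.2 reports that 50 patients were consented to reach 37 evaluable, so accrual seems to have passed the interim. The correction would then serve mainly to record which gate was applied and which patients count toward the monotherapy test. None of this removes the contradiction.

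**Conclusion.** The concern holds. The stage 2 sentence is wrong as written under either reading: it contradicts the Part 1 interim rule, or it contradicts the Part 2 design. The design itself is sound. With the gate on monotherapy CR+PR, the exact type I error is 0.0935 and the power 0.902, and these two figures rest only on the protocol's own inputs. The reading (a) ranges (type I error 0.051 to 0.110 and power 0.44 to 0.94 with the gate replaced) rest on an assumed combination response rate of 5% to 30% and on independence. The reading (b) differences (0.540 against 0.440 at a 5% response rate, 0.069 against 0.028 at 20%) need only the binomial model. The text should be corrected because it is the decision rule for the primary objective, although the intent can be inferred. The mismatch between clinical response and clinical benefit is secondary.

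**What to change.** 1. Reword the stage 2 gate, for example: *If at least 1 of the first 12 evaluable patients treated with trametinib monotherapy has an objective response (CR+PR), 25 more will be accrued, giving 37 evaluable patients.*
2. Reword the failing outcome so that it counts objective responses: *3 or fewer with CR+PR*.
3. If the sentence was meant for patients enrolled directly on the combination, move it to Part 2 and reconcile it with the 16+16 rule, including the final cut-off.
4. Under either reading, reconcile the Part 2 population. The Part 1 paragraph sends later enrollees to the combination after a failed interim, while the Part 2 paragraph describes only patients who progress on monotherapy.
5. If the interim has already taken place, record which gate was applied.

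Items 1 and 2 are wording changes in Section 13.3, with no effect on sample size or procedures. Item 3 is also wording only if 16+16 is kept. Choosing 12+25 for the combination would move the Part 2 total from 32 to 37, and its error rates would have to be restated. Items 4 and 5 are clarifications of text.
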